Phone Visit and Performance Check (2 weeks after baseline)

1. Study staff will contact the subject and parent/guardian to see how well the subject is adapting to the GSM brace and remind the subject/parent to remove the temperature monitor from the brace and send by courier overnight to the study site.
2. Safety Check: Query for adverse events and other issues
3. Performance Check – to ensure adherence to prescribed number of hours per day in the GSM brace:
 1. If any problems are noted during the phone contact the PI will determine whether adjustments to the brace could alleviate the issues and, if so, ask the subject return to clinic
 2. If the temperature monitor data indicate the subject is wearing the GSM brace an average of 2 or more hours less per day than prescribed
 - a. The PI will determine whether adjustments to the brace could alleviate the issues and have the subject return to clinic; if not, the subject will exit the study and return to their current TLSO
 - b. If after adjustments to the brace, the subject feels that the brace is still incompatible with the prescribed wear time, the subject will exit the study and return to their current TLSO

Phone Visits (Weeks 4, 6, 8, and 10 after baseline)

1. Study staff will contact the subject and parent/guardian to see how well the subject is adapting to the GSM brace and remind the subject/parent to continue completion and return of the diaries to the study site in the prepaid envelopes.
2. Safety Check: Query for adverse events and other issues

Visit 3 (3-4 months after baseline, approximately 1 hour)

1. Standing coronal full-spine radiographs out of the brace and measurement of the Cobb angle
2. Download of temperature monitor data from GSM brace
3. Collection of GSM Brace Diary
4. Completion of the Brace Questionnaire and the Italian Spine Youth Quality of Life (ISYQOL) questionnaire
5. Completion of GSM App Feedback Questionnaire (optional)
6. Safety Check: Query for adverse events and other issues
7. Performance Check:
 - a. If the Cobb angle measures no more than 10 degrees greater than that obtained from the subject's most recent out of brace radiograph (prior to enrollment), we will conclude the curve is stable or has progressed within the expected limit. If not, the subject will resume use of the TLSO.
 - b. If curve stabilization is seen, subjects may opt to continue the GSM brace or resume use of their TLSO based on subject and parent preferences.

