Ongoing Evaluations after Visit 3 (following the standard-of-care until GSM brace is discontinued)

For subjects continuing to use the GSM brace after Visit 3: Subject clinical care and evaluations (x-rays, clinical exams) after Visit 3 will be limited to that typically performed as the standard of care (SOC). The exception to the SOC will be the administration of the BrQ and ISYQOL at the end of treatment, ongoing monitoring and recording of AE's discovered during routine clinic visits or other communications, and temperature monitoring (at sites where this is not typically SOC). Clinical and radiographic data from these visits will be collected for study purposes (height, weight, onset of menses, Cobb angle(s), kyphosis, lordosis, coronal and sagittal balance, apical vertebral rotation, in-brace Cobb angle(s), and skeletal maturity indicators) as available.

GSM brace treatment will be discontinued using individualized SOC parameters such as Cobb angle and skeletal maturity indicators, at which time the subject will exit the study.

Exit From Study

Subjects will exit the study upon occurrence of the following events

1. Visit 2. GSM in-brace Cobb is $>10^\circ$ more than the TSO in-brace Cobb
2. Subject not wearing or tolerating GSM brace (per temperature monitor reading 2 weeks after baseline, or at any time during study period)
3. Visit 3. GSM out-of-brace Cobb indicates curve progression
4. GSM brace is discontinued using standard of care criteria

Additional Information on Assessments

Radiographs and Assessments: When available, radiographs will be obtained using the EOS® Imaging system Micro Dose protocol. The EOS® system provides low dose, full body, stereoradiographic images of patients in a functional position. It is a bi-planar device using two perpendicular fan beams of X-rays and proprietary detectors that travel vertically while scanning the patient. In a few seconds, the EOS® exam produces two simultaneous frontal and lateral, low dose images of the whole body or an anatomical segment. The Micro Dose option for pediatric follow up exams further reduces the radiation exposure. <http://www.eos-imaging.com/us/professionals/eos/eos>.

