7 STUDY ASSESSMENTS AND PROCEDURES

7.1 PERFORMANCE ASSESSMENTS

1. Primary performance measures
 1. Visit 2 GSM in-brace Cobb angle compared to that in the TLSO at baseline
 2. Visit 3 out of brace Cobb angle compared to measurements from the most recent out of brace radiograph
 3. Average hours of GSM brace wear per day over the 3-month trial period (temperature monitor data)
 4. Change in scores on the Brace Questionnaire and the ISYQOL
2. Secondary measures
 1. Vital capacity and range-of-motion relative to that obtained in the TLSO at Visit 1
 2. Accelerometer data (obtained from an embedded sensor in the GSM brace) as an estimate of the average hours of wear per day (to be validated by comparison with temperature monitor data)

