8 STATISTICAL CONSIDERATIONS

8.1 SAMPLE SIZE DETERMINATION

Study-wide, recruitment will continue until at least 10 but no more than 30 subjects have completed 3 months in the GSM brace. The final sample size will depend on an ongoing examination of the results, patient comments, input from medical monitor and the discretion of the sponsor. Therefore, if a subject exits the study prior to that point, another subject will be enrolled. The sample size is appropriate for initial field testing of this device and no sample size calculations were conducted.

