8.4 STATISTICAL ANALYSES

This is a pilot study and no formal hypothesis testing will be done.

Descriptive statistics of selected variables will be calculated.

Primary Aims

1. Safety of the GSM brace: Summary of all adverse events; number and nature of adjustments made to the GSM brace
2. Performance of the GSM brace:
 - a. Difference between in-brace Cobb angle measurements obtained in each brace
 - b. Difference in out of brace Cobb angles (pre- and 3 months post-GSM brace)
 - c. Average hours of wear per day relative to the prescription and to historical wear data (from chart and temperature monitor)
 - d. Change in BrQ and ISYQOL scores baseline to 3-month visit; summary of GSM acceptability during various activities and qualitative analysis of free text entries recorded in GSM Brace Diary

Secondary Aims

1. Difference in range-of-motion testing between TLSO and GSM brace
2. Difference in vital capacity testing between TLSO and GSM brace

3. Correlation of accelerometer data and temperature monitor data; development and testing of an algorithm to convert accelerometer data to an estimate of the average hours of wear per day.

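### Subjects who leave before Visit 3 have no BrQ or ISYQOL score in the GSM brace, so the primary quality-of-life change describes only those who stayed

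*Combined protocol and SAP*

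**What the plan says.** **Exit.** Section 5.1.2 (Exit From Study) lists "Subject not wearing or tolerating GSM brace (per temperature monitor reading 2 weeks after baseline, or at any time during study period". At the 2-week check, average wear at least 2 hours a day below prescription leads the investigator to consider adjusting the brace; "if not, the subject will exit the study and return to their current TLSO". A subject also exits if she still finds the brace incompatible with the prescribed hours after adjustment. Section 6.1 repeats the wear rule and requires no follow-up once the brace is stopped. Section 6.2 lets a subject leave by choice at any time.

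**Replacement.** Section 8.1 sets the target as 10 to 30 subjects who have completed 3 months, and "if a subject exits the study prior to that point, another subject will be enrolled".

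**Questionnaires.** BrQ and ISYQOL are given at Baseline Visit 1 and at Visit 3. A later administration is described thus: "The exception to the SOC will be the administration of the BrQ and ISYQOL at the end of treatment". It applies to subjects who keep the GSM brace after Visit 3. Section 8.4, primary aim 2d, analyses "Change in BrQ and ISYQOL scores baseline to 3-month visit", together with a summary of the brace diary.

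**Wear.** Section 7.1 defines "Average hours of GSM brace wear per day over the 3-month trial period (temperature monitor data". Section 8.4, aim 2c, reports "Average hours of wear per day relative to the prescription and to historical wear data (from chart and temperature monitor". The brace carries two temperature monitors. One is removed and couriered to the site at 2 weeks. For the other, the Visit 3 list has "Download of temperature monitor data from GSM brace".

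**The concern.** Whether a subject reaches the follow-up questionnaire depends partly on how well she tolerates the brace. Those who cannot wear it leave and are replaced, and they are not asked for the score that would record their experience. The reported change then answers the quality-of-life question among subjects for whom the brace was acceptable enough to keep.

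Adherence and patient-reported acceptability are primary performance objectives (section 2). Section 1.1 argues that better acceptability will improve adherence and so justify a pivotal trial, and section 3.1 gives supporting that trial as a purpose of the pilot. The analysis is descriptive, so its value depends on knowing which subjects the summaries describe. Section 8.4 names no analysis set, does not say how exits are handled, and asks for no count of subjects fitted, exited and completed.

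**Working it through.** The plan has no figure to reproduce: section 8.1 says no sample size calculation was made, and no exit rate or SD is given. The check is therefore of the schedule first, then of scale under stated assumptions.

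**What exists for a subject who exits before Visit 3**

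| Item | Available? | Source |
|---|---|---|
| BrQ/ISYQOL in the TLSO | Yes | 5.1.2, Baseline Visit 1 |
| BrQ/ISYQOL in the GSM brace | None scheduled | 5.1.2, Visit 3 and later only |
| Wear, weeks 0 to 2 | Yes, if still in the study at the 2-week check | 5.1.2, Phone Visit |
| Wear after week 2 | Second monitor; download listed only at Visit 3 | 5.1.2, Visit 3 |
| Diary | Partly; mailed in during the trial | 5.1.2, Phone Visits; 8.4, aim 2d |
| Adverse events | Yes, up to exit | 5.1.2; 8.4, aim 1 |

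The change in aim 2d needs a Visit 3 score, so it cannot be computed for early exits.

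**Scale for quality of life**

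Let d be the fraction of fitted subjects who exit early, and Mc and Me the mean changes in completers and in exits, had the exits been scored. The mean over all fitted is (1 − d)·Mc + d·Me, so the completers' mean is too high by d·(Mc − Me). The number fitted for n completers is n/(1 − d), rounded up. Both d and the gap Mc − Me are assumptions.

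| d | Fitted for 10 completers | Fitted for 30 completers | Error, gap 0.5 SD | Error, gap 1 SD |
|---|---|---|---|---|
| 10% | 12 | 34 | 0.05 SD | 0.10 SD |
| 20% | 13 | 38 | 0.10 SD | 0.20 SD |
| 30% | 15 | 43 | 0.15 SD | 0.30 SD |
| 40% | 17 | 50 | 0.20 SD | 0.40 SD |

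For comparison, the standard error of a mean change is 1/√10 = 0.32 SD with 10 completers and 1/√30 = 0.18 SD with 30. More completers shrink the standard error but not the selection error.

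**Scale for wear, if aim 2c is computed in completers only**

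Inputs: prescription 18 h, the low end of the range in the brace customization section, so the limit is 18 − 2 = 16 h. Assumed: mean wear 13 h (the median in the earlier bracing trial cited in section 1.2, not this trial's), SD s = 3 to 5 h, correlation 0.8 between week-2 and 3-month GSM wear, and a share e of below-limit subjects who exit.

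- With z = (16 − 13)/s, the fraction below the limit is P = Φ(z), and e·P exit.
- Week-2 excess in those retained = e·s·φ(z)/(1 − e·P). The 3-month excess is 0.8 times that.
- For s = 4: z = 0.75, P = 0.773, φ = 0.301. With e = 0.25: 0.25 × 4 × 0.301/0.807 = 0.37, times 0.8 = 0.30 h/day. With e = 0.5: 0.602/0.613 = 0.98, times 0.8 = 0.79 h/day.
- Over s = 3 to 5: 0.18 to 0.41 h/day (e = 0.25) and 0.50 to 1.05 h/day (e = 0.5). With a 22 h prescription: 0.02 to 0.19 and 0.06 to 0.55.
- For GSM minus own TLSO wear, the factor 0.8 becomes 0.8 − r, where r is the correlation of week-2 GSM wear with TLSO wear. At r = 0.5 the error is 0.07 to 0.39 h/day; at r = 0.8 it is zero.
- The standard error s/√n is 0.95 to 1.58 h with 10 completers and 0.55 to 0.91 h with 30.

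**The case against.** The strongest reply has four parts.

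*Exits are not invisible.* A reader might infer that no wear is recorded for subjects who leave. The documents do not support that: the 2-week exit is itself triggered by a monitor that is returned and read. A reader might also infer that acceptability is known only for those who stayed. That goes too far as well. The daily diary covers pain, discomfort and everyday activities, is mailed in during the trial and is part of aim 2d, and the safety aim summarises all adverse events and brace adjustments. This part stands. It narrows the gap to the two questionnaires, the second monitor and the unstated handling of partial wear in aim 2c.

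*The size is assumption throughout.* This also stands. Low wear alone does not cause exit, because adjustment is tried first, and section 6.2 has staff work to keep subjects on protocol. Nothing in the documents supports any particular exit fraction. With 10 completers, every wear error shown at 18 h is below its standard error.

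*Wear in all fitted subjects is not free of error either.* This is correct. If an exit contributes only her week-2 wear, then under the same model the all-fitted mean is off by −(1 − 0.8)·e·s·φ(z), which is −0.04 to −0.17 h/day. That is a reason to show it beside the completers' mean, not in its place.

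*This is a descriptive pilot with own-control comparisons.* No error rate or power is affected, and section 8.1 openly counts completers. But own-control comparison does not restore a missing follow-up score, and the diary and adverse event summaries do not yield the BrQ/ISYQOL change that section 7.1 names as a primary measure.

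**Conclusion.** The point holds for quality of life. As scheduled, the primary BrQ/ISYQOL change can describe only subjects who reached Visit 3, while those removed for low wear or intolerance, or leaving by choice, are replaced. The likely direction favours the GSM brace. This rests on the assumption that exits would have shown a worse change from their own TLSO score; if they would not, the error is nil. With 20% exits and a gap of 0.5 to 1 SD, the completers' mean is 0.1 to 0.2 SD too good. That is an illustration, not an estimate.

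For wear the finding is narrower: the second monitor has no scheduled download at an early exit, and section 8.4 does not say whether partial wear enters aim 2c. A reader might infer that the wear comparison with the TLSO must favour the GSM brace. The documents do not establish that: section 8.4 does not restrict aim 2c to completers, and the within-subject error can be zero.

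The consequence is for interpretation of the pilot, not for its validity as a safety and feasibility study.

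**What to change.** Keep the exit rule, which protects patients.

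- **Section 5.1.2 (visit procedures and Exit From Study):** at any exit before Visit 3, request BrQ and ISYQOL, by mail or when the brace is returned, and download the temperature monitor still in the brace.
- **Section 8.4:** report the numbers fitted, exited under each rule and completed. Report average wear to exit or Visit 3 for all fitted subjects alongside completers, each against prescription and the subject's own TLSO history. Show exit questionnaire scores separately from 3-month scores, because the time in the brace differs.

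The cost is about 5 minutes of existing questionnaires and one download per exit, with no extra subjects or radiographs. Exit scores will come at different times and cannot be pooled with the 3-month change. Some will still be missing, since section 6.3 makes completion voluntary.

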5.1.2 BRACE CUSTOMIZATION, DOSING AND ADMINISTRATION

The GSM braces will be provided directly to the research team by the company at no cost. Each GSM brace will be custom-fabricated via computer-assisted design using the 3D torso scans and a treatment plan (e.g. placement of corrective forces) devised by the treating orthotist as inputs. The brace components are then assembled. Once assembled, the GSM brace will be fit to the subject by representatives of the manufacturer and in consultation with the treating orthotist.

The GSM brace will be prescribed for the same number of hours per day as was the TLSO (generally 18-22 hours per day, individualized based on patient characteristics). Subjects and the family will be shown how to don and doff the brace, how to remove the temperature monitor, and how to exchange and recharge the battery in the GSM sensor board.

5.2 RISK/BENEFIT ASSESSMENT

5.2.1 KNOWN POTENTIAL RISKS

GSM brace: The GSM brace is a non-significant risk device. The FDA defines a significant risk device under 21 CFR 812.3(m) as:

- 1) Is intended as an implant and presents a potential for serious risk to the health, safety, or welfare of a subject;
- 2) Is purported or represented to be for use supporting or sustaining human life and presents a potential for serious risk to the health, safety, or welfare of a subject;

- 3) Is for a use of substantial importance in diagnosing, curing, mitigating, or treating disease, or otherwise preventing impairment of human health and presents a potential for serious risk to the health, safety, or welfare of a subject; or
- 4) Otherwise presents a potential for serious risk to the health, safety, or welfare of a subject

A non-significant risk device is any device that does not meet those criteria. While the device is intended for treating the disease of scoliosis, as are TLSO's, the GSM is not an implant and does not meet the criteria defined in 1 and 2 above. The FDA defines serious risk as potential harm to subjects that could be life-threatening, could result in permanent impairment of a body function, or permanent damage to body structure, or could necessitate medical or surgical intervention to preclude permanent impairment of a body function or permanent damage to body structure. There are no risks associated with this device that could be categorized as serious.

The GSM Dynamic Orthosis is a brace worn externally over the torso of a patient. It has been designed to provide forces of similar magnitude to current standard-of-care braces.

There are no known or suspected risks directly associated with the GSM brace. The performance and safety checks built into the protocol should theoretically insure that use of the GSM brace does not adversely affect the longer-term outcome relative to what was anticipated if only the TLSO was used. However, it is difficult to predict the results of a TLSO for any individual patient and we cannot know with any certainty, given the design of this pilot study, whether or not the GSM brace influences the risk of a successful outcome.

Rare adverse events have been reported related to the use of TLSOs.⁷ Most events involve loss of skin integrity (rash, bruise, irritation) due to pressure from the brace on the skin. Some change in the skin is expected in response to the corrective forces, but loss of integrity should not occur. The risk of these events will be mitigated by careful fitting of the GSM brace and by advising subjects to immediately report any areas of discomfort so the brace can be adjusted. In addition, patients using rigid TLSOs have reported issues with body image and self-esteem, depression and anxiety, although it is not clear that these concerns are directly related to brace wear or to the diagnosis itself. There is no reason to believe that these events or concerns would be any more frequent or severe during the use of the GSM brace, and may be less frequent. Subjects will be followed closely via phone calls every 2 weeks and queried about concerns/events related to brace wear.

Study-related Radiation: All subjects will have research-related coronal radiographs while 1) wearing their TLSO at baseline, 2) in the GSM brace after 1 week of wear, and 3) out of the brace after 3 months of wear. Three additional in-brace coronal radiographs may be obtained at the discretion of the orthotist or investigator in order to maximize the fit, correction, and comfort of the brace and/or check the effect of brace modifications. The total number of research-related radiographs will not exceed 6.

Other than ionizing radiation, here are no valid and reliable methods currently available to directly assess the spine's response to a scoliosis brace. The frequency of radiographs during brace treatment for AIS varies, but in general, radiographs are obtained prior to initiation of a brace, in the brace anywhere from the day the brace is fit to 6 months afterward, and then every 4-6 months until criteria for brace discontinuation is met. Since subjects will enter this study at different times during their treatment, we cannot anticipate which, if any, of the radiographs obtained in this study should be considered standard of care. Therefore, all radiographs obtained between consent and Visit 3 will be considered study-related.

A urine pregnancy test will be administered to all subjects who are of child-bearing potential. If the test is positive, the subject will exit the study.

When available, participating sites should obtain the study radiographs using the EOS® Micro Dose protocol. Use of this protocol results in significantly decreased radiation exposure to the subject relative to standard digital radiography. Comparisons of the EOS® Micro Dose protocol with digital radiography indicate a significant decrease in radiation exposure (0.02 mGy vs. 1.66 mGy;³² 2.6 μ SV vs. 67.5 μ SV³³) for a full spine coronal plane radiograph. Attached correspondence from the University of Iowa Medical Radiation Protection Committee (advisory to the University of Iowa Institutional Review Board) estimates 1 coronal full spine radiograph using the EOS® Micro Dose protocol would expose the subject to an effective dose equivalent of 0.25 mrem, which is about equal to the average environmental radiation everyone experiences in 1 day. The maximum study-related effective dose equivalent will total approximately 3 mrem of radiation. The maximum total exposure for all study-related radiation is approximately equal to the amount of radiation everyone experiences in 3 days.

**Participating sites who are not using the EOS® Micro Dose protocol will be responsible for calculating the amount of research-related radiation and the potential risks, to include this information in IRB/human subjects research application materials, and to relate this information to the subject via the informed consent document as required by the IRB or equivalent review board.*

Spirometry: There are no risks associated with use of the Spiropet spirometer. Subjects may stop the testing at any time if they feel uncomfortable.

Only for subjects enrolled at sites where compensation will come directly from the Sponsor/U of Iowa: If subjects agree to share their name and contact information with the University of Iowa for purposes of compensation, this information will be given to [name] over the phone or via fax.

